## Part 2 (Open-label Extension)

For assessments performed in the open-label extension the baseline is defined to be the Day 190 assessment.

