14.2.3. Efficacy Data

Part 1

Individual efficacy data will be listed. For muscle strength (as assessed by handheld dynamometer), the MVIC value will be derived for each side and the average maximum peak force value [from the left and right sides] will be determined for each individual patient and scheduled time. For the MVIC value for each side treated as well as the average from the left and right sides, CMTES2 score, CMT-HI total score and selected subscale scores, and motor

Clinical Study Protocol Study A083-03 Revision: 03

function test assessments, raw and changes from baseline (percent and absolute change) for the injected muscle will be summarized for each scheduled time using descriptive statistics. For each efficacy variable, a repeated-measures ANCOVA model will be fitted and least square mean estimates of the effect of ACE-083 and the corresponding 90% confidence intervals will be provided for the percent change from baseline. For muscle strength parameters, the change from the screening to baseline value will serve as the control for each cohort and will be summarized together with post-baseline data. Baseline is defined as the last non-missing value prior to dosing. Theoretically, this should be the Day 1 predose value. Other strength measurements will be summarized and reported similarly. Additional analyses may be performed as appropriate.

Analyses described above concerning selected motor function test assessments related to gait will be considered as exploratory.

Part 2

Individual efficacy data will be listed. For muscle strength, the MVIC value and decimal MMT-MRC score will be derived for each side and the average [from the left and right sides] will be determined for each individual patient and scheduled time.

Double-blind, placebo-controlled phase

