For each pharmacodynamic variable, raw data and changes (percent and/or absolute change) from the start of the open-label extension (Day 190) will be summarized by treatment for each scheduled time using descriptive statistics.

Additional analyses may be performed as appropriate.

Open-label extension vs. double-blind placebo-controlled phase

For each of the following pharmacodynamic variables, a mixed model will be used to assess the effect ACE-083 administered during the open-label extension [Day 358 vs. Day 190 (2nd 6 months)] compared to the effect of the treatment administered in the double-blind placebo-controlled phase [Day 190 vs. pre-first treatment baseline (1st 6 months)] separately for those receiving placebo during the double-blind phase as well as for those receiving ACE-083 during the double-blind phase:

- Percent change in total muscle volume (average of right and left sides) during the openlabel extension vs. double-blind phase
- Percent change in intramuscular fat fraction (average of right and left sides) during the open-label extension vs. double-blind phase
- Percent change in contractile muscle fraction (average of right and left sides) during the open-label extension vs. double-blind phase
- Percent change in contractile muscle volume (average of right and left sides) during the open-label extension vs. double-blind phase

Least squares estimates of this effect and 95% confidence intervals will be provided. In addition, point estimates of this effect and corresponding 95% confidence intervals will be provided for patients having dorsiflexion MRC-MMT grade of 4- to 4+ on both sides.

Additional analyses may be performed as appropriate.

Clinical Study Protocol Study A083-03 Revision: 03 14.2.4.1. Pooled Analyses

If applicable, similar analyses will be performed for pooled Part 1 and 2 data for patients at the same dose level. Pooling by the estimated local dose of ACE-083 in the injected muscle (i.e., mg ACE-083/g muscle) may also be performed. Details of these analyses will be included in the SAP.

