14.2.5. Safety Data

Unless otherwise specified, safety data will be summarized using descriptive statistics and individual safety data will be listed. AEs will be coded using the Medical Dictionary for Regulatory Activities. Incidence of treatment-emergent AEs will be presented by system organ class and preferred term. AE incidence rates will be described by cohort with and without regard to causality. The frequency of occurrence of overall toxicity, categorized by toxicity grades (NCI-CTCAE, current version) will be summarized. Change from baseline in clinical laboratory parameters, ECG, and vital signs will be summarized across time. Shift tables will be presented for selected laboratory parameters and vital signs. Physical examination results will be presented in listings.

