**Part 2**

Unless otherwise stated, tables and figures will be presented using one or more of the following as shown below, depending on what is being summarized/analyzed.

Part 2 – Double-blind period

Placebo	ACE-083	Overall
---------	---------	---------

Part 2 – Open-label period – by treatment group sequence

ACE-083→ACE-083	Placebo→ACE-083
-----------------	-----------------

Part 2 – Open-label period – Pooled across treatment group sequence

ACE-083
---------

Listings will contain the treatment groups shown above however, there will be no “Overall” group.

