**4.1.4. Definitions of Baseline****Part 1 and Part 2 (Double-blind Phase)**

Baseline is defined to be the last non-missing assessment prior to the first dose of study drug administration. Theoretically, this could be either the Screening assessment or the Day 1 assessment depending on the parameter.

The first dose date will serve as the reference from which the non-missing pre-treatment values would be identified. For patients that are randomized (applicable to patients participating in Part 2) but do not receive any study drug administration, the date of randomization will be the baseline reference.

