#### 4.10.2. Clinical Laboratory Evaluations

Individual clinical laboratory data will be listed.

The following table lists the planned clinical laboratory assessments:

Type of Assessment	Details
Hematology	Hemoglobin, hematocrit, platelet count, red blood cell count, white blood cell (WBC) count, and WBC differential
Chemistry	AST, ALT, lactate dehydrogenase (LDH) and isoenzymes 1-5, gamma-glutamyl transpeptidase (GGT), blood urea nitrogen (BUN), creatinine, creatine kinase (CK), myoglobin, aldolase, sodium, potassium, glucose, albumin, total bilirubin
Urine	Urinalysis by dipstick analysis (pH, specific gravity, protein, myoglobin, glucose, ketones, blood, leukocyte esterase, and nitrite)

In addition to the tests listed below, a urine pregnancy test is performed on all females of childbearing potential according to scheduled times listed in the protocol.

Descriptive statistics of raw data and change from baseline data will be provided by treatment group for each scheduled time.

Plots of mean  $\pm$  SEM will be provided for raw data and change from baseline data for the following selected laboratory data: hemoglobin, glucose, aldolase, blood urea nitrogen (BUN), creatinine kinase (CK), creatinine, and myoglobin.

Additional analyses may be performed as appropriate.

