#### Vital Signs

Individual vital sign data will be listed.

Vital sign parameters consist of weight, heart rate, systolic and diastolic blood pressure.

Descriptive statistics will be provided for raw data and absolute change from baseline by scheduled time for each treatment group. Post-dose recheck values will not be used for calculation of descriptive statistics.

Additional analyses may be performed as appropriate.

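### As written, the SAP measures open-label laboratory and vital-sign change from Day 190, so patients on ACE-083 throughout have no planned change summary over all 17 doses (minor; a free improvement)

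*SAP*

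**What the plan says.** SAP 4.1.4 has two baseline rules. For Part 1 and the double-blind phase of Part 2: "Baseline is defined to be the last non-missing assessment prior to the first dose of study drug administration". For the extension: "For assessments performed in the open-label extension the baseline is defined to be the Day 190 assessment". The second rule is not limited to efficacy or pharmacodynamic variables.

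The safety sections rely on these general rules. For laboratory tests (SAP 4.10.2): "Descriptive statistics of raw data and change from baseline data will be provided by treatment group for each scheduled time". For vital signs: "Descriptive statistics will be provided for raw data and absolute change from baseline by scheduled time for each treatment group". Neither names a reference visit.

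Biomarkers sit under pharmacodynamic data. SAP 4.8.1.2 names CTX and hemoglobin, and hemoglobin is also a safety laboratory test in 4.10.2. In the open-label extension the SAP summarises biomarker changes from baseline by treatment sequence and adds summaries pooled over the two sequences.

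The protocol uses Day 190 as a named reference for open-label efficacy and pharmacodynamic data: changes "from the start of the open-label extension (Day 190) will be summarized by treatment for each scheduled time using descriptive statistics" (14.2.3, with matching text in 14.2.4). For open-label pharmacodynamic variables, 14.2.4 asks for percent change from baseline and, separately, change from Day 190. For safety, 14.2.5 says only: "Change from baseline in clinical laboratory parameters, ECG, and vital signs will be summarized across time".

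**The concern.** Day 190 is the Dose 10 visit, and study procedures precede dosing. In the placebo-to-ACE-083 sequence it is normally the last drug-free value, so it is the right reference. In the continuous ACE-083 sequence it already reflects doses 1 to 9. Any laboratory or vital-sign shift in the first six months becomes part of their open-label baseline, and a shift that has levelled off appears as no change from Day 190 onward.

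The double-blind ACE-083 arm is the only group with laboratory and vital-sign data over 17 doses. The natural summary of cumulative exposure is within-patient change from before the first dose, and the SAP does not plan it for open-label visits. Where sequences are pooled, as for biomarkers, a single column averages change from an on-drug value with change from a drug-free one.

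**Working it through.** **Dose count.** Dosing is every 21 days from Day 1 to Day 337 (protocol schedule of events).
- All doses: (337 − 1)/21 + 1 = 17.
- Before Day 190, the last being Day 169: (169 − 1)/21 + 1 = 9.
- Day 190 to Day 337: (337 − 190)/21 + 1 = 8.

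This reproduces the 9 + 8 = 17 of protocol 10.1.

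**Interval covered at Day 358 in the continuous ACE-083 sequence.**
- From the pre-first-dose baseline, taking it at Day 1: 358 − 1 = 357 days (51 weeks), 17 doses.
- From Day 190: 358 − 190 = 168 days (24 weeks), 8 doses.
- Ratio: 168/357 = 8/17 = 0.47.

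**Share of the 12-month change that remains visible.** The documents give no time course, so this is an assumed range. Let f(t) be the mean shift t days after first ACE-083, either linear or f(t) = 1 − exp(−kt) with k = ln 2/(7h) for a half-time of h weeks. The visible share is [f(357) − f(189)]/f(357).

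**Pooled summary.** Assume equal sequences (20 and 20) and the same time course in both. At Day 358 the newly exposed have changed by f(168) and the continuing patients by f(357) − f(189). In the exponential case the latter equals exp(−189k) × f(168). Since 189 days is 27 weeks, the pooled mean as a fraction of the newly exposed change is (1 + 2^(−27/h))/2. In the linear case both groups change by eight doses' worth, so nothing is diluted.

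| Assumed time course | Share of 12-month change visible, continuous ACE-083 | Pooled change as share of newly exposed change |
|---|---|---|
| Linear | 47% | 100% |
| Half-time 26 weeks | 31% | 74% |
| Half-time 12 weeks | 17% | 61% |
| Half-time 6 weeks | 4% | 52% |
| Complete by Day 190 | about 0% | about 50% |

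**What the reset does not touch.** Treatment-emergent adverse events run from first dose to the end of follow-up (SAP 4.10.1). ADA prevalence covers the whole study (SAP 4.10.3). Part 2 ECGs are scheduled only at screening, Day 1 and Day 85, so there is no open-label ECG change to distort. Raw values at each visit and the double-blind change tables remain.

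**The case against.** The strongest reply is that the SAP never says in terms that safety laboratories are reset. Its open-label efficacy and MRI sections name Day 190 explicitly; 4.10.2 does not. That is fair: the reach to safety data follows from an unrestricted general rule plus silence in 4.10. But the rule is unrestricted, and the other baseline is headed for Part 1 and the double-blind phase only, so a programmer following the text would use Day 190. If the sponsor intends otherwise, the text still needs to say so.

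Second, little information is lost. Among patients seen at both visits, mean 12-month change equals the difference in raw means, and also the sum of the two six-month changes. This stands for means. It does not recover the SD, median, minimum or maximum of individual changes, or keep the patient set constant once some drop out. In the plateau case the shift would also appear in the double-blind tables against concurrent placebo, which is better evidence than an uncontrolled 12-month change.

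Three stronger readings are tempting and not supported.
- *An unlisted departure from the protocol for safety data.* Protocol 14.2.5 defines no baseline for open-label safety visits. The definition "Baseline is defined as the last non-missing value prior to dosing" stands in the Part 1 text of the efficacy section and does not govern Part 2 safety. SAP Section 5 therefore had no safety change to list.
- *Pooled laboratory and vital-sign tables.* The layout "Part 2 – Open-label period – Pooled across treatment group sequence" in SAP 4.1.3 is one of several, to be used according to what is summarised, and does not commit safety tables to pooling. The planned pooling is for biomarkers, and by-sequence summaries accompany it.
- *Loss of the trial's evidence on longer-term tolerability.* Adverse events and ADA prevalence are not reset.

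**Conclusion.** The point holds as a minor one. Following SAP 4.1.4 as written, open-label laboratory and vital-sign change in up to 20 continuously treated patients covers doses 10 to 17 only, and no within-patient change over all 17 doses is planned. For biomarkers, including hemoglobin, the planned pooled change mixes two kinds of baseline. Protocol 14.2.4 asks for both references for open-label pharmacodynamic variables, while the SAP's general rule yields only one.

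The size is conditional: between about 0% and 47% of the 12-month change is visible over the assumed time courses, and the pooled figure lies between about 50% and 100% of the newly exposed change. The two losses do not move in step. Under linear build-up 53% of the cumulative change is hidden (1 − 0.47) but the pooled summary is not diluted; the halving requires a shift that is complete by Day 190. These are descriptive summaries, and the primary analysis is unaffected.

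**What to change.** In SAP 4.1.4, add that for open-label laboratory, vital-sign and biomarker summaries:
- change is also shown, by sequence, from the last available value before the first ACE-083 dose: the double-blind baseline for ACE-083→ACE-083, and normally Day 190 for Placebo→ACE-083;
- change from Day 190 is kept alongside it;
- any pooled ACE-083 change summary uses the pre-ACE-083 baseline.

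Anchoring on the first ACE-083 dose also settles the case, allowed for in SAP 4.1.5, of a Day 190 assessment made up to 7 days after the Day 190 dose. A pooled value at Day 358 will still combine patients after 17 doses with patients after 8, so the by-sequence columns should be the main display.

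The cost is one definition and one extra set of change columns from data already collected. Study conduct does not change.

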### 4.1.5. Data Handling Conventions

Unless otherwise stated or indicated:

- Individual data for all patients will be presented in data listings, sorted by “Study Part” (Part 1 or Part 2), “Treatment Group”, and “Patient Number”;
- For any parameter analyzed, only observations from visits and/or time points planned in the protocol will be used in descriptive statistics. An exception to this rule is for a baseline assessment. Should an unscheduled assessment be taken after the scheduled baseline assessment but before the first dose of study medication, then the unscheduled assessment may be used as the baseline;
- For variables where the Day 1 assessment is defined as the baseline, should an individual patient have a Day 1 assessment after having received their first dose, then an unscheduled assessment may be used as the baseline, provided that the unscheduled assessment was done prior to first dose.
- Should a patient be assigned to the wrong CMT-type stratum (e.g. a CMT1 patient assigned to the CMTX stratum or a CMTX patient assigned to the CMT1 stratum), the patient’s true CMT-type (CMT1 or CMTX) will be used in statistical models where CMT-type is used as a covariate.
- With the exception of what is described in the preceding bullet, unscheduled assessments will not be collectively summarized in summary tables or figures; however, these data will appear in individual patient listings.
- For adverse events where the assessment of “Relationship to study drug” is missing, it will be assumed that the adverse event is “Probably Related” to study drug.
- For selected pharmacodynamic and efficacy data, tests of statistical hypotheses and estimation using the end-of-treatment visit or the Day 190 visit (Part 2 double-blind component), multiple imputation for missing data will be performed. Additional techniques for handling missing data may also be considered and evaluated.
- If a patient has a Day 190 assessment performed after having received the Day 190 dose (first dose in the open-label phase), then the Day 190 assessment for that patient will be included in statistical analyses of Day 190 data only if the difference between the Day 190 assessment and the Day 190 dose date is less than or equal to 7 days.
- Descriptive statistics for quantitative parameters will be provided using number of observations (N), mean, standard deviation (SD), standard error of the mean (SEM), median, minimum and maximum;
- Should it be necessary to convert duration in days to duration in months, the duration in days will be divided by 30.417 (365/12) to calculate duration in months.

- Descriptive statistics for qualitative parameters will be provided using frequencies (N) and percentages (%).
- If the result of a continuous variable contains nonnumeric values (e.g. ‘<X’ or ‘>X’), the imputed values used for the descriptive statistics will be determined by considering the following rules:
  - If the value is ‘<X’, the value used will be X/2;
  - If the value is ‘>X’, the value used will be X.
- Concerning the determination of absolute and percent change from baseline for data such as MRI and muscle strength where assessments are reported separately for the left and right sides and the average absolute and/or percent change from baseline is needed, the absolute and/or percent change is determined for the left and right sides separately and then averaged. The “average” represents the “average” absolute (or percent) change from baseline for the left and right sides. For MRI and muscle strength data, should a patient have an MRI and/or strength assessment on one side (i.e. right side) but not the other side at an individual time point, the value for the average absolute (or percent) change from baseline for that patient and time point will be the absolute (or percent) change from the side from which the MRI and/or strength assessment was obtained.

## 4.2. Analysis Population

The analysis populations include the following:

- Full Analysis Set: Part 1 – All patients enrolled in the study receiving at least one dose of ACE-083. Part 2 – All patients randomized who have received at least one dose of study drug (includes placebo);
- Safety Set: All patients enrolled/randomized in the study who have received at least one dose of study drug (includes placebo);
- Per Protocol Set: All patients enrolled/randomized in the study who have received at least one dose of study drug (includes placebo) with no data or study procedural related issues that would otherwise impact the interpretability of the efficacy and/or pharmacodynamic data.

Such issues include but are not necessarily limited to:

- Patients who discontinue the study prior to the Dose 3 Day 43 visit; these patients may have been replaced per protocol
- Patients whose Day 1 MRI or Day 190 MRI was done 7 or more days following study drug administration
- Patients who did not receive the full study drug administration planned per protocol at all injection sites on any or both sides (right or left) for 2 or more consecutive visits for reasons other than dose reductions for the safety of the patient or feasibility concern (i.e., the site intended to administer the full dose but was unable).

- Patients whose Screening cumulative distance walked at 6 minutes is greater than 500 meters or less than 150 meters.

A review of the patient data will be performed and a list of patients to be excluded from the Per Protocol Set along with the reason for exclusion will be completed before the data is locked and unblinded.

Statistical analyses of efficacy and pharmacodynamics data will be performed on the Per Protocol Set (primary analysis population) and the Full Analysis Set (secondary analysis population). Analyses of safety data will be performed on the Safety Set. Should the statistical analysis populations be identical (e.g., Full Analysis Set = Per Protocol Set), statistical analyses will not be duplicated or repeated.

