If the Day 190 cumulative distance recorded at 6 minutes has no missing data, then the ANCOVA models described above will be used for analysis. If missing data is present, a standard multiple imputation with the above ANCOVA models will be used for analysis as described in [Section 4.11.1](#).

A mixed model repeated measures (MMRM) analysis will be performed to assess the sensitivity to the ANCOVA analyses described above. An unstructured covariance structure will be used to model the within-patient covariance across visits. Other covariance structures will be considered if the unstructured covariance fails. The covariates to be included consist of all of the covariates described above for the ANCOVA with the addition of the following additional covariates: VISIT where VISIT represents the scheduled visit day post first dose of MRI assessment and TREATMENT\*VISIT.

Similar to what was described for the ANCOVA analyses above, if missing data is present, a standard multiple imputation with the above MMRM model will be used for analysis as described in Section 4.11.1.

The findings from the ANCOVA model described above will be considered primary.

The analyses described above will also be done for the absolute change from baseline.

The analyses described above will also be repeated for the Full Analysis Set.

Additional analyses may be performed as appropriate.

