### **4.8.2.2. Part 2**

#### **4.8.2.2.1. Double-Blind Period**

##### **MRI: Total Muscle Volume (TMV)**

Individual total muscle volume data will be listed.

Descriptive statistics will be provided by treatment group and scheduled time for raw data and changes from baseline (absolute and percent change) for each side [left and right]. The average absolute change and average of the percent change for the left and right sides will also be provided.

The primary pharmacodynamic analysis will consist of an ANCOVA in order to assess the effect of ACE-083 on the Day 190 average percent change from baseline for the left and right sides. Covariates to be included into the model are TREATMENT, BASELINE, and CMT-TYPE where:

- TREATMENT represents the treatment group (ACE-083 or placebo)
- BASELINE represents the baseline total muscle volume (average of left and right sides)
- CMT-TYPE refers to the type of CMT (e.g. CMT1 or CMTX)

The effect of ACE-083 versus placebo will be estimated using the ANCOVA model described above and tested using a 0.1 significance level (2-sided). The least-square mean estimate along

with the corresponding 90% confidence interval will be provided. In addition, the 95% confidence interval will also be provided.

If the Day 190 TMV has no missing data, then the above ANCOVA model will be used for analysis. If missing data is present, a standard multiple imputation with the above ANCOVA model will be used for analysis as described in [Section 4.11.1](#).

A mixed model repeated measures (MMRM) analysis will be performed to assess the sensitivity to the ANCOVA analysis described above. An unstructured covariance structure will be used to model the within-patient covariance across visits. Other covariance structures will be considered if the unstructured covariance fails. The covariates to be included consist of all of the covariates described above for the ANCOVA with the addition of the following additional covariates: VISIT where VISIT represents the scheduled visit day post first dose of MRI assessment and TREATMENT\*VISIT.

Similar to what was described for the ANCOVA analysis above, if missing data is present, a standard multiple imputation with the above MMRM model will be used for analysis as described in Section 4.11.1.

The statistical analyses described above will be done on the Per Protocol Set and will be considered primary. The analyses described above will also be repeated for the Full Analysis Set.

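### A late Day 1 or Day 190 MRI removes the whole patient from the Per Protocol Set, so on-time non-MRI data leave the primary efficacy analyses; the rule also conflicts with SAP 4.1.5 at exactly 7 days

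*SAP*

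**What the plan says.** SAP 4.2 defines a single Per Protocol Set. It restricts the set to dosed patients without problems that would affect interpretation of the efficacy and/or pharmacodynamic data, and gives examples introduced by "Such issues include but are not necessarily limited to". One example is "Patients whose Day 1 MRI or Day 190 MRI was done 7 or more days following study drug administration". The unit is the patient: before lock and unblinding, "a list of patients to be excluded from the Per Protocol Set along with the reason for exclusion will be completed". Efficacy and pharmacodynamic analyses "will be performed on the Per Protocol Set (primary analysis population) and the Full Analysis Set (secondary analysis population"). There is no endpoint-specific version of the set.

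The endpoint sections follow this. Berg, falls, CMTES2, gait and total muscle volume (TMV) each state that the Per Protocol Set is primary. The 6-minute walk and 10-meter walk/run name the Full Analysis Set only as a repeat. MVIC and CMT-HI name no set, so 4.2 governs.

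Other parts of the SAP deal with the same event at the level of the measurement. Under 4.1.5, a Day 190 assessment made after the Day 190 dose "will be included in statistical analyses of Day 190 data only if the difference" from the dose date is at most 7 days. For TMV, "If missing data is present, a standard multiple imputation with the above ANCOVA model will be used for analysis"; the 6-minute walk section says the same: "If missing data is present, a standard multiple imputation with the above ANCOVA models will be used for analysis". Section 4.11.1 fills the gap from previous time points under a missing-at-random assumption.

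The protocol's own Per Protocol definition asked for at least one post-baseline MRI. The SAP does not carry that condition over, and SAP section 5 declares that the set was redefined.

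**The concern.** The date of a scan does not affect the validity of a walk test, a dynamometer reading, a questionnaire or a fall count. The 6MWD model contains treatment, height, CMT type and baseline, with no MRI term. The visit windows also differ: Protocol Appendix 1 allows the MRI up to 5 days before the dose and function and strength tests up to 24 hours before it. An MRI can therefore slip while everything else is done on time. Under 4.2 such a patient leaves the primary analysis of every endpoint, including 6MWD, for which the plan makes its own power claim.

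The stakes are loss of valid randomised data from the analyses labelled primary, through a post-randomisation exclusion unrelated to those endpoints, and different treatment of patients whose usable information is the same.

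**Working it through.** **Reading used.** I take the dose in the 4.2 criterion to be the dose given at the same visit (Day 1 or Day 190), in line with 4.1.5.

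**1. Day 190 scan.** Take a patient with Day 43 and Day 106 scans, on-time function and strength tests before the Day 190 dose, and no other ground for exclusion.

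| Day 190 MRI, days after the Day 190 dose | Scan under 4.1.5 | Patient under 4.2 | Non-MRI data in primary analyses |
|---|---|---|---|
| 1 to 6 | used | in | kept |
| exactly 7 | usable (limit is at most 7) | out (limit is 7 or more) | removed |
| more than 7 | not used, so missing and imputable | out | removed |
| no scan taken | missing and imputable | no listed criterion applies | kept, unless the data review adds a reason |

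Row 2 is a direct conflict. In row 3 the measurement rule already keeps the late scan out of the analysis, so 4.2 adds only the removal of the Day 43 and Day 106 scans and all non-MRI data. Rows 3 and 4 carry the same usable MRI information but are treated differently under the listed criteria. By comparison, a 6MWD or MVIC taken more than 7 days after the dose is dropped and imputed, and no listed criterion removes the patient for it.

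**2. Day 1 scan.** SAP 4.1.4 requires baseline to precede the first dose, and the Part 2 schedule has no screening MRI. A patient scanned only after dosing generally has no TMV baseline, so no percent change at any visit; losing that patient from the MRI analyses is justified. The exception is an unscheduled pre-dose scan, which 4.1.5 accepts as baseline. Timed function, strength, balance and gait, CMTES2 and CMT-HI are all scheduled at screening, so non-MRI baselines do not depend on the MRI. A Day 1 scan 1 to 6 days after dosing leaves the patient in the set although 4.1.4 does not accept that scan as baseline, so 4.2 is not a reliable test of baseline validity either.

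**3. The plan's sample size.** Inputs from SAP 4.1.1: difference 10, SD 10 per group, two-sided alpha 0.10, 1:1 allocation, standard t-test, the same for TMV and 6MWD. Power is the probability that a noncentral t with n1 + n2 − 2 degrees of freedom and noncentrality 10 / (10 × √(1/n1 + 1/n2)) exceeds the two-sided 10% critical value in absolute size. For 18 and 18: noncentrality 1/√(2/18) = 3.000, 34 degrees of freedom, critical value 1.691, power 0.9023. The stated 90% with 36 patients reproduces, as does 36/0.90 = 40 randomised.

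**4. Cost of exclusions.** The number of late scans is an assumption, because the documents give none.

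| Patients per arm | Power |
|---|---|
| 20 / 20 | 0.9279 |
| 20 / 19 | 0.9220 |
| 19 / 19 | 0.9160 |
| 18 / 18 | 0.9023 |
| 18 / 17 | 0.8944 |
| 17 / 17 | 0.8865 |
| 16 / 16 | 0.8684 |

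One exclusion costs 0.9279 − 0.9220 = 0.0059 from the full 40, or 0.9023 − 0.8944 = 0.0079 from 36. Two per arm from 18 and 18 costs 0.9023 − 0.8684 = 0.0339.

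**The case against.** The best defence has four parts.

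First, every efficacy and pharmacodynamic analysis is also run on the Full Analysis Set, where the late-MRI patient keeps all on-time data and 4.1.5 deals with the scan. A reader might infer that the function data are lost; they are not. They leave one of two pre-specified analyses, but it is the one designated primary.

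Second, a reader might infer that a patient with no Day 190 MRI is certain to stay in the Per Protocol Set. The SAP does not say so. No listed criterion removes that patient, but the list is open-ended and a data review precedes lock. The asymmetry is a feature of the written criteria, not a guaranteed outcome.

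Third, the event should be rare and its effect small. The Day 190 scan is due before the dose, so one 7 or more days after it is a gross deviation. Patients who drop out after Day 43 are not removed by the early-discontinuation criterion and most of their missing endpoints are imputed, so the working number may be nearer 40 than 36, where one or two exclusions leave power above 90%. This stands.

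Fourth, a common set keeps MRI and function tables on the same patients, and the exclusion list is fixed before unblinding. Both are real advantages. Blinded selection limits selective exclusion, and nothing in the documents ties scan lateness to treatment, so a claim of bias would go beyond them. Neither advantage explains why an MRI date should decide whether a walk test counts.

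**Conclusion.** The point holds as a matter of data handling. SAP 4.2 takes valid strength, function, CMT-HI, CMTES2 and falls data out of the primary analyses for an MRI-only reason. For Day 190 it largely repeats a measurement-level rule the SAP already has, and at exactly 7 days it contradicts that rule.

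Two further readings should be avoided. The loss of usable Day 43 and Day 106 TMV data concerns the Day 190 limb; after a late Day 1 scan there is generally no baseline from which to use them. And a late non-MRI value is not always imputed: MVIC, the walk tests, Berg, CMT-HI and CMTES2 are, while the MMT score, falls and gait are not.

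The effect on power is small, about 0.6 to 0.8 points for one excluded patient. That figure assumes the design difference and SD and a complete-data t-test; the planned ANCOVA with imputation was not modelled. The total effect depends on a count of late scans that the documents do not give.

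**What to change.** In SAP 4.2, restrict the MRI-timing criterion to the MRI endpoints:

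- A Day 190 MRI taken too late is set to missing for MRI endpoints and imputed under 4.11.1 from the patient's earlier scans.
- A patient with no valid pre-dose MRI is left out of the MRI analyses only.
- In both cases the patient stays in the Per Protocol Set for strength, function, CMT-HI, CMTES2, falls and the other non-MRI endpoints.
- Use one 7-day cut-off. The simplest way is for 4.2 to refer to the limit in 4.1.5.
- State whether a patient with no Day 190 MRI remains in the set, so that this is not left to the open-ended list.

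The cost is a short wording change before lock. Patient numbers may then differ between MRI and function tables, which a footnote can explain.
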